6.2. Primary analysis

The tested null hypothesis is that the mean quality of life (measured by the EQ5D-5L) for patients receiving the 3D intervention is the same as for those receiving usual care at 15 months follow up.

Primary analysis will take the form of mixed-effects multivariable linear regression, adjusted for practice (random effect to account for clustering), minimisation variables (practice size and practice deprivation score) and patient baseline EQ5D-5L. The results will be presented as the difference between group means, corresponding 95% confidence interval and P-value. The intra-class correlation (ICC) will also be reported, with a 95% confidence interval. Practices/patients will be analysed in the groups to which they were allocated and missing data will be imputed (section 3.3).

The distribution of EQ5D-5L and model residuals will be examined (a suitable transformation or a boot-strapped 95% confidence interval accounting for clustering²¹ will be considered if necessary).

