2.6. Randomisation procedures

To minimise post-randomisation selection bias, practices will not be randomised until after patients have been identified and after the initial patient invitations have been mailed.

Practices will be randomised using an algorithm written in advance by the Bristol Randomised Trials Collaboration (BRTC, UKCRC registration ID: 2) on a 1:1 ratio to receive either the intervention or continue care as usual (control group). Randomisation will be stratified by recruiting centre (Bristol, Manchester, and Glasgow) and minimised by practice deprivation level and practice size. Practices within each area will be randomized using a block size of two (one randomized to the 3D intervention and the other to usual care), to ensure balance across the treatment arms given the relatively small number of practices. Within each centre, each block of two practices will be randomized at the same time in the following way.

Within each centre, the initial block of two will be randomized using simple randomization, such that one is allocated to intervention and the other control. For each subsequent block of practices, an algorithm (written within Stata specifically for this study) will determine the allocation of the two practices which creates the best balance in terms of size and deprivation and then weights the randomisation in favour of this allocation (rather than being deterministic); the weights being determined by the degree of imbalance in terms of size and deprivation (see Table 1 and example below).

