3.3. Procedures for missing data

Missing data may arise as some participants may not return their questionnaires. It is anticipated that proportions with missing data will be similar between the two randomization arms but this will be examined and reported. Baseline characteristics will be compared between participants with and without 15-month follow-up data. In all tables missing data will be indicated by footnotes.

The primary analysis for EQ5D-5L (section 6.2) will include the full analysis set (section 3.1), including all patients in the groups to which they were allocated and imputing missing data. Reasons for missingness will be explored. Missing data will be imputed using multiple imputation techniques such as multiple imputation by chained equations (MICE). Imputation models will include baseline, 9 month and 15 month EQ5D-5L data (as available), intervention arm, stratifying/minimisation variables, as well as other variables such as baseline covariates and auxiliary covariates that are informative of missingness. To allow for clustering in Stata, imputations will be used for the primary analysis and the economic evaluation if possible. The influence of missing data on the primary analysis will be investigated in sensitivity analyses using complete case data only (section 6.5).

The analyses of secondary outcomes will use complete case data only. The only exception to this is for secondary outcomes derived from several items within a validated questionnaire, where questionnaire guidelines specifically state that an overall score can be derived even in the presence of missing data for one (or more) item(s). For example, for HADS anxiety and depression scores, questionnaire guidelines state that the score for a single missing item from a subscale is inferred by using the mean of the remaining six items; however, if more than one item is missing from that subscale the overall score is missing (and the observation excluded from the analysis). The numbers (percentage) of missing data will be presented in tables of secondary outcomes.

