3.4. Study centre effects

Randomisation is at the general practice (centre) level; the effect of practice will be taken into account as a random effect in multi-level regression models.

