6.3. Secondary analyses

All analyses of secondary outcomes will be adjusted for the baseline measure of the outcome (if available) and minimisation variables. Patient level analyses will also adjust for practice (as a random effect). All secondary outcomes will be considered at 9 and 15 months.

The list of variables and planned models of analysis are given in the table below. Distributional checks will be carried out for all outcomes and the most appropriate models selected (for example, for ordinal outcomes mixed-effects ordered logistic models will be performed and assumptions regarding the ordinal nature of responses tested; if not valid alternative multinomial models will be employed). The effect, 95% confidence interval and P value will be reported for each model along with the ICC if possible.

Table 6: Planned analyses - Patient level secondary outcomes

Outcomes	Type of variable	Type of model ¹
CARE measure of relational empathy (GP)	Continuous	Mixed-effects linear regression
CARE measure of relational empathy (nurse)	Continuous	Mixed-effects linear regression
Care related to patients' priorities (LTC6)	Discrete (ordinal)	Mixed-effects ordered logistic regression
Care which is joined up (LTC6)	Discrete (ordinal)	Mixed-effects ordered logistic regression
PACIC measure of chronic disease management	Continuous	Mixed-effects linear regression
Overall satisfaction	Discrete (ordinal)	Mixed-effects ordered logistic regression
EQ5D-5L	Continuous	Mixed-effects linear regression
Self-rated health	Discrete (ordinal)	Mixed-effects ordered logistic regression
Bayliss measure of illness burden	Continuous	Mixed-effects linear regression
HADS Anxiety score	Continuous	Mixed-effects linear regression
HADS Depression score	Continuous	Mixed-effects linear regression
Multimorbidity Treatment Burden Questionnaire	Continuous	Mixed-effects linear regression
Medication adherence: MMAS-8	Continuous	Mixed-effects linear regression
Number of drugs prescribed	Count data	Poisson regression random effects
Number of high risk prescribing indicators	Count data	Poisson regression random effects
Continuity of care - COC index	Continuous	Mixed-effects linear regression
Continuity of care - Visit Entropy	Continuous	Mixed-effects linear regression
Quality of disease management	Continuous	Mixed-effects linear regression
Number of hospital admissions	Count data	Poisson regression random effects
Number of outpatient attendances	Count data	Poisson regression random effects

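### Recruiting centre stratifies the randomisation but is left out of the primary and patient-level secondary models, so the standard error is too large if areas still differ after adjustment

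*SAP*

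**What the plan says.** On the design, SAP section 2.6 states: "Randomisation will be stratified by recruiting centre (Bristol, Manchester, and Glasgow) and minimised by practice deprivation level and practice size". It goes on: "Practices within each area will be randomized using a block size of two (one randomized to the 3D intervention and the other to usual care"). Each pair therefore puts one practice in each arm within an area, and the arms are balanced on area by construction.

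On the analysis, section 6.2 describes a mixed-effects linear regression "adjusted for practice (random effect to account for clustering), minimisation variables (practice size and practice deprivation score) and patient baseline EQ5D-5L". The bracket spells out the minimisation variables as size and deprivation, so the phrase cannot be read to include recruiting centre. Section 6.3 follows the same pattern: "All analyses of secondary outcomes will be adjusted for the baseline measure of the outcome (if available) and minimisation variables", and "Patient level analyses will also adjust for practice (as a random effect"). Section 6.4 lists model types for the comparative process measures but names no covariates. The CACE analysis in section 6.5.3 reuses the variables of the primary analysis.

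The one section whose title suggests that area is handled, 3.4 (Study centre effects), says: "Randomisation is at the general practice (centre) level; the effect of practice will be taken into account as a random effect in multi-level regression models". Sections 2.3 and 2.6 use *centre* for the three recruiting areas; section 3.4 uses it for the practice.

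**The concern.** Stratified allocation removes between-area differences from the chance variation of the treatment effect, because every area contributes equally many practices to each arm. The analysis gets the benefit only if the model also contains area. Otherwise the model counts area differences as if they could have fallen unevenly between the arms. With a practice random effect and no area term, they are absorbed mainly into the practice variance. The standard error is then larger than the true sampling variation, and the ICC that section 6.2 promises to report mixes practice and area differences.

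This costs precision; it does not introduce bias. Precision matters here because section 2.7 concedes that the trial may be underpowered for a minimally important difference below 0.074, while intending to interpret the result against smaller published values (0.051 and 0.063).

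Nothing elsewhere in the SAP puts area back. Section 6.5.1 adds covariates only where important baseline imbalance is found, and area is balanced by design. Sections 6.5.2 to 6.5.6 do not mention it.

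**Working it through.** **Inputs.** From SAP section 2.7: 32 practices, 1382 recruited, 80% followed up, ICC 0.03, effect size 0.274 SD, SD 0.27, 5% significance (taken as two-sided). From section 2.6: 1:1 allocation, so 16 practices per arm. Not in the documents, and therefore assumed as a range: *s*, the share of between-practice variance that lies between the three areas.

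**Reproducing the plan's figure.**
- Analysed per practice: m = 1382 × 0.8 / 32 = 34.55.
- Design effect: 1 + (34.55 − 1) × 0.03 = 2.0065.
- Effective number per arm: (1382 × 0.8 / 2) / 2.0065 = 275.5.
- Power for 0.274 SD: 89.5%, which agrees with the stated figure of around 90%.

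**Standard error with and without area.** In SD units, with total variance 1:
- Area omitted: variance of the difference = (4/32) × [0.03 + 0.97/34.55] = 0.125 × 0.05808; SE = 0.0852.
- Area included: variance of the difference = (4/32) × [0.03(1 − s) + 0.97/34.55].
- Ratio R = SE omitted / SE included. True type I error of the nominal 5% test with area omitted = 2 × [1 − Φ(1.96 R)].

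| s (assumed) | SE, area included | R | 95% CI half-width on EQ5D, omitted → included | True type I error, area omitted |
|---|---|---|---|---|
| 0 | 0.0852 | 1.00 | 0.045 → 0.045 | 5.0% |
| 0.10 | 0.0830 | 1.03 | 0.045 → 0.044 | 4.4% |
| 0.25 | 0.0795 | 1.07 | 0.045 → 0.042 | 3.6% |

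The half-width is 1.96 × SE × 0.27.

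**Reported ICC.** With area omitted it is 0.03. With area in the model it would be 0.027 / (0.027 + 0.97) = 0.027 at s = 0.10, and 0.0225 / (0.0225 + 0.97) = 0.023 at s = 0.25.

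**Simulation check.** 32 equal-sized practices were simulated as practice means, in three areas (an assumed split of 12, 10 and 10) with arms balanced within area and 8000 runs per scenario. Coverage of the 95% interval under the null was:
- area omitted: 94.6%, 95.5% and 96.7% at s = 0, 0.10 and 0.25;
- area included: 94.6%, 95.0% and 95.2%.

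At s = 0.25 the mean interval width under the null fell from 0.346 to 0.323 SD when area was added. At s = 0, adding area changed power from 87.96% to 87.80%, about 0.2 points. That is the price of two degrees of freedom if areas turn out not to differ.

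**The case against.** The strongest reply is that the size of the effect is unknown and may be nil. The primary model already contains baseline EQ5D-5L, practice size and practice deprivation, which may account for most of what separates the areas. The SAP gives no between-area figure. This stands: the omission is a fact of the text, but a statement that the intervals *are* too wide would go beyond it.

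Four stronger readings may tempt a reader, and the documents support none of them.

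- **A gain in power.** The 89.5% comes from a design calculation with no baseline adjustment, whereas the planned model adjusts for baseline EQ5D-5L and should start from higher power. Setting 89.5% against a figure with area included does not describe the planned analysis, so no power gain is claimed.
- **A large effect.** At s = 0.50 the ratio R would be 1.16. That needs a between-area SD of √0.015 × 0.27 = 0.033 on EQ5D, remaining after adjustment for the same measure at baseline. This is extreme beside minimally important differences of 0.051 and 0.063.
- **A clash with the imputation model.** Section 3.3 imputes with "intervention arm, stratifying/minimisation variables", so area enters there but not in the analysis. An imputation model richer than the analysis model is normal practice. The harmful case is the reverse.
- **Area-dependent data.** The items unavailable in Scotland (Tables 5 and 9) are intervention-arm descriptives with no comparative model. The footnote to Table 2 on CSU data or questionnaire does not tie availability to area.

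It is also fair to say that the error is conservative: false positives are not increased.

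**Conclusion.** The point holds as a correctable loss of precision. The only stratification factor is missing from the primary and patient-level secondary models as specified, and section 3.4 obscures this by using *centre* for practice. The primary estimate is unbiased. If areas differ after adjustment, the standard error is too large, the test is conservative and the reported ICC absorbs area differences. The excess in the standard error is about 3% at s = 0.10 and 7% at s = 0.25, and zero if areas do not differ.

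These figures assume equal practice sizes, the plan's ICC of 0.03 and no baseline adjustment. They apply to the linear primary model; the ordinal and count outcomes share the omission, but its size there has not been worked out. The change is worth making because it costs almost nothing, not because the trial's conclusion is known to be at risk.

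**What to change.** Add recruiting centre (Bristol, Manchester, Glasgow; two indicators) as a fixed effect in:
- the primary model in section 6.2;
- the patient-level secondary models in section 6.3;
- the comparative process models in section 6.4;
- the CACE analysis in section 6.5.3, which reuses the primary variables.

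Reword section 3.4 so that *recruiting centre* means one of the three areas and *practice* means the cluster, and state how each enters the models.

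The carer and death models need not change. Section 2.10.2 describes the carer data as few and exploratory, section 7.1.1 already lists several covariates for deaths, and nothing computed here supports adding two more terms to either.

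The cost is SAP wording and two practice-level degrees of freedom, worth about 0.2 points of power if areas do not differ. No new data are needed, since centre is already recorded for randomisation.

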6.3. Secondary analyses

All analyses of secondary outcomes will be adjusted for the baseline measure of the outcome (if available) and minimisation variables. Patient level analyses will also adjust for practice (as a random effect). All secondary outcomes will be considered at 9 and 15 months.

The list of variables and planned models of analysis are given in the table below. Distributional checks will be carried out for all outcomes and the most appropriate models selected (for example, for ordinal outcomes mixed-effects ordered logistic models will be performed and assumptions regarding the ordinal nature of responses tested; if not valid alternative multinomial models will be employed). The effect, 95% confidence interval and P value will be reported for each model along with the ICC if possible.

Table 6: Planned analyses - Patient level secondary outcomes

Outcomes	Type of variable	Type of model ¹
CARE measure of relational empathy (GP)	Continuous	Mixed-effects linear regression
CARE measure of relational empathy (nurse)	Continuous	Mixed-effects linear regression
Care related to patients' priorities (LTC6)	Discrete (ordinal)	Mixed-effects ordered logistic regression
Care which is joined up (LTC6)	Discrete (ordinal)	Mixed-effects ordered logistic regression
PACIC measure of chronic disease management	Continuous	Mixed-effects linear regression
Overall satisfaction	Discrete (ordinal)	Mixed-effects ordered logistic regression
EQ5D-5L	Continuous	Mixed-effects linear regression
Self-rated health	Discrete (ordinal)	Mixed-effects ordered logistic regression
Bayliss measure of illness burden	Continuous	Mixed-effects linear regression
HADS Anxiety score	Continuous	Mixed-effects linear regression
HADS Depression score	Continuous	Mixed-effects linear regression
Multimorbidity Treatment Burden Questionnaire	Continuous	Mixed-effects linear regression
Medication adherence: MMAS-8	Continuous	Mixed-effects linear regression
Number of drugs prescribed	Count data	Poisson regression random effects
Number of high risk prescribing indicators	Count data	Poisson regression random effects
Continuity of care - COC index	Continuous	Mixed-effects linear regression
Continuity of care - Visit Entropy	Continuous	Mixed-effects linear regression
Quality of disease management	Continuous	Mixed-effects linear regression
Number of hospital admissions	Count data	Poisson regression random effects
Number of outpatient attendances	Count data	Poisson regression random effects

¹Analyses will be dependent on distributional checks

Table 7: Planned analyses - Carer secondary outcomes

Carer secondary outcome	Type of variable	Type of model ¹
Carer experience scale	Continuous	Mixed-effects linear regression
EQ5D-5L carer score	Continuous	Mixed-effects linear regression
Multimorbidity treatment Burden	Continuous	Mixed-effects linear regression
Questionnaire (carers)		

¹Analyses will be dependent on distributional checks

6.4. Process of care measures

Process measure	Type of variable	Type of model ¹
Number of primary care consultations with GP	Count data	Poisson regression random effects
Number of primary care consultations with nurse	Count data	Poisson regression random effects
Mean duration of face to face consultations in surgery with GP	Continuous	Mixed-effects linear regression
Mean duration of face to face consultations in surgery with nurse	Continuous	Mixed-effects linear regression
Number of different review consultations	Count data	Poisson regression random effects
At least one review received	Binary	Mixed-effects logistic regression

Table 8: Planned analyses – Patient level process of care measures

¹Analyses will be dependent on distributional checks

Other process measures collected at 15 months in the intervention group only (reported in Table 5) will be reported with descriptive statistics. For several measures percentages will be reported both as the percentage of all patients recruited to the intervention arm and the percentage of patients receiving at least one nurse or GP review (as appropriate). See Table 9 below.

Table 9: Descriptive statistics - Patient level process of care measures collected in the	
intervention arm only	

Process measure	Type of	Summary	Denominator used in percentage			
	variable	statistics	All patients in intervention arm	All those having at least one nurse review	All those having at least one GP review	
Number of nurse 3D reviews	Ordinal	N (%)	 ✓ 	NA	NA	
Number of GP reviews	Ordinal	N (%)	 ✓ 	NA	NA	
Compliance ¹	Ordinal	N (%)	 ✓ 	NA	NA	
Most important problem noted	Binary	N (%)	✓	\checkmark	NA	
EQ5D pain question noted	Binary	N (%)	NA	\checkmark	NA	
PHQ9 entered	Binary	N (%)	 ✓ 	\checkmark	NA	
Medication reviewed by Pharmacist (at least one comment entered)	Binary	N (%)	1	NA	1	
Medication adherence noted	Binary	N (%)	✓	NA	 ✓ 	
First patient goal noted	Binary	N (%)	✓	NA	 ✓ 	
First plan noted ('what patient can do')	Binary	N (%)	1	NA	1	

First plan noted ('what GP can do')	Binary	N (%)	\checkmark	NA	\checkmark
Patient agenda printed ¹	Binary	N (%)	\checkmark^2	✓ ²	NA
3D plan printed ¹	Binary	N (%)	\checkmark^2	NA	✓ ²
Number of times hospital physician was contacted	Count	Median (IQR)	NA	NA	NA

¹ Data not available in practices in Scotland

² Denominators include only those recruited from England

6.5. Sensitivity analysis

The analyses presented above make a number of assumptions about the data (for example, the treatment groups are balanced, all patients have received the allocated treatment, all patients completed questionnaires at the correct time point). Sensitivity analyses will consider whether the conclusions drawn in the primary analysis are sensitive or robust to different assumptions made.

6.5.1 Baseline imbalance

Baseline characteristics will be compared between the treatment groups and the magnitude of any differences considered in terms of their potential clinical importance (following discussion with clinicians). Where important differences exist, baseline characteristics will be adjusted for in sensitivity analyses.

6.5.2 Missing data

The impact of missing data on the primary analysis will be explored by conducting complete case analyses (using the complete cases data set (see section 3.1).

6.5.3 Non-compliance

If compliance is less than 90% we will also perform a complier average causal effect (CACE) analysis for the primary analysis of EQ5D-5L. Compliers can only be observed amongst those randomized to the 3D arm. Compliance will be defined as 'full' – two GP 3D appointments and two nurse 3D appointments attended; 'partial' – at least one GP or nurse 3D appointment attended but not full compliance; and 'none' – no GP 3D appointment and no nurse 3D appointment attended. These three categories will be compared in terms of key baseline characteristics. Sensitivity analysis considering the complier average causal effect (CACE), will include two analyses with a dichotomous indicator variable for compliance: one analysis will amalgamate patients in the 'full' and 'partial' groups; the other will combine those in the 'none' and 'partial' groups.

The CACE estimates will be obtained using instrumental variable regression including the same variables used in the primary analysis, randomized group as an instrumental variable and the indicator variable for compliance.

6.5.4 Time of questionnaire return

It is likely that there will be variation in the time at which questionnaires are completed. In sensitivity analyses, time of completion will be included as a covariate.

6.5.5 Outliers/influential values

The impact of outliers/influential values will be explored by removal of such observations from the analyses.

6.5.6 Treating deceased patients as missing for EQ5D-5L

As an additional sensitivity analysis, we will investigate the impact of treating the deceased as having a missing score for EQ5D-5L at 15 months rather than imputing a value of zero. This analysis will be performed using the complete case dataset.

6.6. Potential effect modifiers

Potential effect modifiers, selected *a priori* and informed by previous evidence, will be explored using appropriate interaction terms added to the regression models used for the primary analysis. Subgroup analyses of the primary outcome will explore differences in the effectiveness of the 3D intervention compared to usual care according to baseline measures of:

- Participant age (< median / ≥ median of consenting participants);
- Number of long term conditions as defined in section 2.4.3 (< median / ≥ median of consenting participants);
- Deprivation (quartiles of consenting participants);
- Depression alongside physical health problems (presence/absence).

Subgroup analyses are likely to be insufficiently powered since the trial was not powered to specifically test these effects. These subgroup analyses will therefore be hypothesis generating and will focus on interpretation of 95% confidence intervals rather than P-values.

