2.7. Sample size and justification

The study is designed to detect an effect size of 0.274 standard deviations in the primary outcome of the EQ5D-5L. Data about the variability of the new 5 level (5L) version of the EQ5D is currently more limited than for the well-established 3 level (3L) version. The standard deviation of the EQ5D-3L in the UK general population is 0.23, rising to 0.27 in the oldest respondents (aged over 75)³. Hence an effect size of 0.274 would equate to a detectable difference of (0.274*0.27) = 0.074 on the EQ5D-3L, previously deemed to be the minimum important difference (MID)⁴. Although less data is available about the variability in

the 5L version of the EQ5D than the 3L version, it seems wise to use this latest version of the EQ5D as it is likely to have greater sensitivity to change.

Based on data available from our previous studies, we estimate that 2.3% of adult patients will have multi-morbidity in terms of three or more LTCs as defined in this study. This equates to about 108 patients in an average sized practice of 6000 patients i.e. 3456 potentially eligible patients in 32 practices. Assuming 40% of patients agree to participate (n=1382), 80% are followed up to 12 months, and an Intra-Cluster Coefficient (ICC) of 0.03 for clustering at the practice level (based on the WISE trial)⁵ this sample provides around 90% power at a 5% significance level to detect an effect size of 0.274 standard deviations in the EQ5D measure between the intervention and control groups.

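### Section 6.6 explores age, number of long-term conditions and deprivation only through sample-median or quartile groups; continuous interactions would give narrower intervals at almost no cost

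*SAP*

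**What the plan says.** SAP section 6.6 names four baseline modifiers of the primary outcome. Three are ordered measures placed in groups set by the sample:

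- Age is divided in two: "Participant age (< median / ≥ median of consenting participants".
- The count of long-term conditions is divided in two at its sample median, in the same manner as age.
- The third measure is divided in four: "Deprivation (quartiles of consenting participants".

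The remaining modifier, coexisting depression, is coded yes or no and is not at issue.

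Effect modification is to be "explored using appropriate interaction terms added to the regression models used for the primary analysis". The section does not say whether the deprivation quartiles enter as an unordered factor or as a trend. It is open about the limits: "Subgroup analyses are likely to be insufficiently powered since the trial was not powered to specifically test these effects". It labels the results hypothesis generating and says that reporting "will focus on interpretation of 95% confidence intervals rather than P-values".

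**The concern.** Age and number of conditions are ordered numerical measures, and the SAP holds deprivation as a score, at least at practice level (sections 2.6.1 and 6.2). Section 6.6 gives no clinical basis for the cuts, which depend on who consents. Patients just either side of the median are treated as different, and patients far apart within one half as alike.

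If benefit rises or falls steadily with a modifier, grouping discards part of the evidence on that gradient. The plan already expects these analyses to be imprecise and asks readers to rely on the intervals, so an avoidable widening falls on the very quantity to be interpreted. At stake is the chance of seeing a real gradient in benefit with age, number of conditions or deprivation.

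**Working it through.** **Inputs from the SAP (section 2.7).** The plan states "Assuming 40% of patients agree to participate (n=1382), 80% are followed up to 12 months", with 32 practices and ICC 0.03, and claims "around 90% power at a 5% significance level to detect an effect size of 0.274 standard deviations". Allocation is 1:1 (section 2.6).

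**The plan's own figure.** Analysed n = 1382 × 0.8 = 1105.6, or 34.55 per practice. Design effect = 1 + (34.55 − 1) × 0.03 = 2.0065. Effective n per arm = 1105.6 / 2.0065 / 2 = 275.5. Power for 0.274 SD, two-sided 5%, is 0.895, so the stated 90% reproduces. The SAP gives no power or precision figure for the section 6.6 analyses.

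**Assumptions added here.** The SAP gives no age or deprivation distribution and no interaction size. I assume a gradient linear in the modifier, a modifier that varies between patients within practices, and (except where stated) a normal modifier. No variance reduction from baseline EQ5D-5L is taken.

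**Information kept by a median split.** This is the squared correlation between the modifier and its split version.

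| Shape of modifier | Information kept | Lost | Interval ratio, 1/√kept |
|---|---|---|---|
| Uniform | 0.75 | 25% | 1.15 |
| Left-skewed, beta(5,2) | 0.65 | 35% | 1.24 |
| Normal | 2/π = 0.637 | 36% | 1.25 |
| Exponential | 0.48 | 52% | 1.44 |

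**Standard errors.**
- Contrast of the effect between halves: 4 × √(0.97/1105.6) = 0.118 SD.
- Slope of the effect per SD of the modifier: 2 × √(0.97/1105.6) = 0.0592 SD.
- A slope b gives a difference between halves of 2 × √(2/π) × b = 1.596b.

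**Power, median split against continuous (two-sided 5%).**
- Difference 0.274 SD: b = 0.274/1.596 = 0.172. Continuous z = 0.172/0.0592 = 2.90, power 83%. Split z = 0.274/0.118 = 2.31, power 64%. Loss 19 points.
- Difference 0.137 SD: continuous z = 1.45, power 31%. Split z = 1.16, power 21%. Loss 9 points before rounding.
- Difference 0.1 SD: 18% against 13%. Loss 5 points.

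**Deprivation in quartiles.** For a normal modifier, quartiles keep 0.861 of the information with free scores and 0.856 with equally spaced trend scores. The three-degree-of-freedom powers use a noncentral chi-square with noncentrality 0.861 × z².

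| Difference between halves | Continuous | Quartile trend, 1 df | Quartile factor, 3 df |
|---|---|---|---|
| 0.274 SD | 83% | 76% (loss 6) | 61% (loss 22) |
| 0.137 SD | 31% | 27% (loss 4) | 18% (loss 13) |

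Losses are taken before rounding.

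**The case against.** The strongest defence is that section 6.6 is pre-specified, limited to four modifiers, uses interaction terms rather than separate subgroup tests, and declares its low power. It promises exploration through intervals, not tests, so power at the 5% level is not its criterion. Groups are easy to present, and if the effect changes in a step near the median a split loses nothing. All of this stands, and it keeps the point minor. It does not remove it, because the loss also appears as interval width, which is what the plan asks readers to use.

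A reader might infer more than the document supports:

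- **That 36% of the information is lost as a matter of fact.** That figure needs a normal modifier and a linear gradient, and the SAP gives no distributions.
- **That power always falls by 12 to 20 points.** For a normal modifier, the median-split loss reaches that size only when the continuous analysis would have roughly 40% to 95% power. In the low-power setting that the plan describes, it can be under 10 points.
- **That deprivation is committed to a three-degree-of-freedom test.** The wording on interaction terms also permits a trend, for which the loss is small.
- **That the power figures hold for deprivation at practice level.** They assume variation between patients within practices. The SAP's deprivation score is a practice measure in the minimisation and the primary model, and section 6.6 does not say which level the quartiles use. If practice level, these figures do not apply.

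**Conclusion.** The point holds as a cheap improvement, not as an error. Age and number of long-term conditions are examined only by median split and deprivation only by quartiles, with no continuous interaction.

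Under a linear gradient, the avoidable widening of the interval from a median split is about 15% to 25% for uniform to normal shapes, and more under strong skew. For deprivation the cost turns on a coding choice that the plan leaves open. All of these sizes rest on the assumptions listed above. The analyses remain exploratory, and nothing here touches the primary result.

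**What to change.** In section 6.6:

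1. Make arm × age (for example per 10 years), arm × number of long-term conditions and arm × deprivation score continuous interactions in the primary model. If only quartiles of deprivation are held, use a single-degree-of-freedom trend across them.
2. Report each interaction coefficient with its 95% confidence interval as the effect-modification result.
3. Keep the median and quartile groups for displaying subgroup effects and as a check on linearity.
4. State whether deprivation is the patient's or the practice's score.

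The cost is SAP wording and three changed model terms, with no new data. The small downside is the assumed linearity; the retained groups would show a gross departure from it.
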